The reader of this SAP is encouraged to also read the clinical protocol for details on the planned conduct of this study. Operational aspects related to collection and timing of planned clinical assessments are not repeated in this SAP unless relevant to the planned analyses.

¹ International Conference on Harmonization. (1998). Guidance on Statistical Principles. ICH Topic E9 (Statistical Principles for Clinical Trials) (p. 37). London: International Conference on Harmonization.

2. Purpose

This SAP outlines all statistical analyses to be performed on data collected in study SCGAM-04, and the resulting output that will be compiled to support the completion of the Clinical Study Report (CSR).

The planned analyses identified in this SAP will be included in regulatory submissions and/or future manuscripts. Exploratory analyses not necessarily identified in this SAP may be performed to support the clinical development program. Any post-hoc or unplanned analyses performed that are not identified in this SAP will be clearly identified in the respective CSR.

The statistical output provided to the medical writer of the CSR will closely follow the ICH guideline for industry on topic E3 (Structure and Content of Clinical Study Reports²) to facilitate the subsequent compilation of the CSR.

This statistical output will consist of tables, figures and listings, including

- Tables, figures and listings used or referenced in, or appended to the CSR as detailed in the remainder of this SAP (section 14 of the CSR)
 - Demographic data summary figures and tables
 - Efficacy data summary figures and tables
 - Safety data summary figures and tables
- Listings provided as appendices to the CSR
 - Patient data listings (section 16.2 of the CSR)
 - Individual patient data listings (section 16.4 of the CSR) will be covered by inclusion of data files into the electronic submission to the authorities

A detailed list of all tables, figures and listings will be supplied in a separate document later when all feedback from authorities will be available.

² International Conference on Harmonization. (1996). Structure and Content of Clinical Study Reports. Structure and Content of Clinical Study Reports (Guideline for Industry) (S. 37). London: International Conference on Harmonization.

3. Study Objectives and Endpoints

3.1. Study Objectives

3.1.1. Primary Objective

The primary objective of the study is to evaluate the efficacy of *octanorm* in preventing serious bacterial infections (SBI) compared with historical control data.

3.1.2. Secondary Objectives

The secondary objectives of the study are:

- To evaluate the tolerability and safety of *octanorm*.
- To assess the effect of *octanorm* on quality-of-life (QoL) measures.

3.2. Study Endpoints

3.2.1. Primary Endpoint

The primary efficacy endpoint is the rate of SBI (defined as bacteraemia/sepsis, bacterial meningitis, osteomyelitis/septic arthritis, bacterial pneumonia, and visceral abscess) per person-year on treatment.

3.2.2. Secondary Endpoints

Secondary efficacy endpoints are:

- The annual rate of all infections of any kind or seriousness.
- Non-serious infections (total and by category).
- Time to resolution of infections.
- Use of antibiotics (number of days and annual rate).
- Hospitalisations due to infection (number of days and annual rate).
- Episodes of fever.
- Days missed from work/study due to infections and their treatment.
- QoL assessment using the SF-36 Health Survey.
- Trough levels of serum total IgG throughout the study.

Secondary safety endpoints are:

- Occurrence of all treatment emergent AEs (TEAEs) throughout the entire treatment period starting with the first infusion of IMP.
- Proportion of infusions with at least 1 temporally associated AE.
- Occurrence of adverse drug reactions (ADRs).
- Local injection site reactions.
- Vital signs (blood pressure, pulse, body temperature, respiratory rate).
- Laboratory parameters (haematology, clinical chemistry, and viral status).

4. Study Methods

4.1. Overall Study Design and Plan

Study SCGAM-04 is designed as a prospective, open-label, non-controlled, single-arm, multicentre phase 3 study with an 8 weeks wash-in/wash-out period, followed by a 6-month efficacy period. Each patient who stays in the study for the whole period will receive 32 weekly subcutaneous (sc) infusions of *octanorm*.

Only patients suffering from PI who are on IVIG treatment may be enrolled. The study will be conducted at approximately 5 study sites in Russia.

Patients will be treated weekly with *octanorm*, either at the investigation site (for at least the first 4 infusions and every 4 weeks thereafter) or else at home.

Before starting home treatment, a diary will be provided to the patients for documenting the date, volume and speed of infusion, occurrence of infections, AEs and local tissue reactions at injection sites, missed days from work/study, inpatient hospital stays, and any changes in concomitant therapies between visits.

A final examination will be performed 1 week after the end of the last infusion, or 1 week after premature withdrawal of a patient from the study, with a telephone follow-up 3 weeks later.

4.2. Selection of Study Population

The study population consists of adult patients (≥ 18 years and ≤ 70 years) of both sexes with a confirmed diagnosis of PI who require immunoglobulin replacement therapy due to hypogammaglobulinaemia or agammaglobulinaemia. All patients must have at least 4 infusions on regular and stable treatment with an intravenous immunoglobulin (IVIG) prior to entering the study. Please refer to the protocol for a complete list of all inclusion and exclusion criteria.

5. Sequence of Planned Analyses

5.1. Final Analyses and Reporting

As stated in section 4.1, each patient is treated with *octanorm* over a total period of approximately 32 weeks; one week after the last infusion a follow-up visit is performed. Once the last patient has completed the study, data validation will be completed and the database will be locked according to the applicable standard operating procedures. This process includes a data review, the identification and classification of any protocol deviations, and thus the patient disposition with respect to the analysis populations as detailed in section 7. All final, planned, analyses identified in the protocol and in this SAP will be performed only after the last patient has completed the study, the subject disposition has been agreed and documented, and the final SAP has been approved.

Key statistics and study results will be made available to the study team following database lock and prior to completion of the final CSR by means of tables, figures and listings.

Any post-hoc, exploratory analyses completed to support planned study analyses, which were not identified in the final SAP, will be documented and reported in appendices to the CSR. Any results from these unplanned analyses will also be clearly identified in the text of the CSR.

No interim analysis is planned for this study.

6. Sample Size Determination

This uncontrolled study is designed to obtain data on SBI rates and IgG trough levels in PI patients in Russia, along with clinical safety and efficacy data. The sample size of approximately 20 to 25 evaluable patients will provide local data to supplement the PK data from the SCGAM-01 study that is compliant with the CHMP recommendations for this indication (CHMP Note for Guidance EMA/CHMP/BPWP/94033/2007 rev. 2). No formal sample size calculation is provided.

No attempts will be made for a balanced inclusion of male and female patients.

6.1. Patient Replacement Policy

Patients withdrawn from the study because of safety or efficacy reasons will not be replaced.

Patients withdrawn from the study for any other reason, e.g., major protocol violation, pregnancy or administrative reasons will also not be replaced. However, if the number of withdrawals exceeds the limit of 15%, the sponsor will assess the situation and decide on a possible replacement policy.

Patients who do not satisfy specific entry criteria during screening may be rescreened following discussion of the individual case with the sponsor.

6.2. Premature Termination of the Study

Both, the responsible investigators and the sponsor, reserve the right to terminate the study as a whole or centre-wise at any time. Should this be necessary, the procedures will be arranged on an individual study basis after review and consultation by both parties. In terminating the study, the sponsor and the investigator will ensure that adequate consideration is given to the protection of the patients' interests. Premature termination will be notified in accordance with applicable regulatory requirements. Please refer to the protocol for further details on premature termination.

7. Analysis Populations

The following populations will be considered for the statistical analysis:

The safety set (SAF) consists of all patients who received at least part of one infusion of *octanorm*; it is the set of patients exposed to treatment.

The full analysis set (FAS) consists of all patients of the safety set who satisfy all major eligibility criteria and for whom any post-baseline data is available. It is the set of eligible patients with treatment effects measured, according to the intention-to-treat (ITT) principle.

The per-protocol (PP) set consists of all patients of the FA set excluding those patients with major protocol deviations which may have an impact on the analysis of efficacy. This is the set of patients who participated in the trial as intended and for whom efficacy can be evaluated as planned.

All protocol deviations documented during the conduct of the study or identified at the data review process prior to database lock will be reviewed and classified as minor or major and with respect to their significance for the planned analyses. Only significant protocol deviations with the potential to affect the study results or to invalidate the interpretation of the data obtained will lead to exclusion of subjects from the PP set. This classification of protocol deviations is the joint responsibility of the clinical study manager, the study statistician, and Octapharma's responsible medical expert, and will be performed and documented before the database is locked and the statistical analyses are performed.

Protocol deviations to be considered will include (but will not be limited to):

- Violations of the study entry criteria.
- Administration of any other blood or plasma-derived product or of any other immunoglobulin preparations during the SCGAM-04 study.
- Any forbidden concomitant medication (please refer to section 4.2.2 of the protocol).
- Failure to attend two scheduled consecutive visits OR three or more scheduled visits during the study for reasons other than clinical reasons.

Analysis of the safety endpoints will be based on the SAF.

Efficacy endpoints will be analyzed on basis of the FAS.

Any analysis might be repeated on basis of the PP analysis set if indicated by the data or in case the PP population differs from the FAS by 3 patients or more, to allow for an assessment of the robustness of the results with respect to protocol violations.

8. General Issues for Statistical Analysis

Descriptive summaries will be presented for each of the primary and secondary endpoint variables.

Continuous, quantitative variable summaries will in general include the number of patients with non-missing values (N), mean, standard deviation, median, minimum and maximum, 1st and 3rd quartile.

Categorical, qualitative variable summaries will include the frequency and percentage of patients who are in the particular category. In general the denominator for the percentage calculation will be based upon the total number of patients in the analysis population unless otherwise specified.

8.1. Withdrawals

Patients who withdraw from the study prematurely will be considered in all data presentations for which they contribute data; in particular for the analysis of annual rates they will be considered with their actual observation periods.

8.2. Handling of Missing Data

In general, missing data will not be imputed. Calculations pertaining to person-year computations will be based on observed values only.

For missing weight measurements the last available body weight will be used for all calculations related to dosing (last observation carried forward, LOCF); in individual patient data listings missing data will however not be replaced by imputed values.

No analyses of the patterns of missing data will be done.

For adverse events the following will be applied:

An Adverse Event (AE) is defined as treatment-emergent, if first onset or worsening is after start of the first infusion of *octanorm*; if the start date and time of an AE are partially or completely missing, the AE will be assumed to be treatment-emergent if it cannot be definitely shown that the AE did not occur or worsen after start of the first infusion of *octanorm* (worst case approach). Missing dates and times will not be replaced.

For medications the following will be applied: A medication will be assumed to be concomitant if it cannot be definitely shown that the medication was not administered during the *octanorm* treatment period as defined in section 8.4 below. Missing dates will not be replaced.

8.3. Derived and Computed Variables

The following derived and computed variables have been initially identified as important for the analysis of the primary and secondary target variables. It is expected that additional variables will be required. The SAP will not be amended for additional variables that are not related to the primary target or key secondary target variables. Any additional derived or computed variables will be identified and documented in the statistical programs that create the analysis files. If the SAP is not amended, further derivations related to primary and secondary target variables will be described in the CSR.

- **Age** will be derived according to the usual definition that a person is n years old until she or he has completed her or his $(n+1)^{\text{th}}$ year of life, using the date of informed consent as the reference date. This is also the definition that will be applied for evaluation of the age related inclusion criteria. [Unit: years]

- **Body Mass Index:** $BMI = (\text{Body weight}) / \text{Height}^2$ [Unit: kg/m²]
- The **octanorm treatment period** is defined as the period between the day of first treatment with study drug to the end of the observation period. This will usually be the termination visit.
- Because the octanorm treatment period also includes the wash-in/wash-out phase it is necessary to also define a **primary treatment period**, which starts on the date of the 9th infusion of octanorm (Visit 7/week9) and ends together with the octanorm treatment period defined above. This ensures that any occurring infection can be attributed to a steady-state treatment with octanorm unambiguously. [Unit: years]
- The **rate of serious bacterial infections** per year during regularly repeated treatment with *octanorm* will be calculated as $r = (\text{Total number of serious bacterial infections occurring in the primary treatment periods}) / (\text{Sum of primary treatment periods})$ [Unit: 1/years]
- The **rate of other infections** will be derived using the same method
- The **rate of infusions with one or more temporally associated AEs** will be calculated for each patient as $r = (\text{Number of infusions with one or more temporally associated AEs}) / (\text{Number of infusions started})$. An AE is defined as a temporally associated if, and only if, the onset (or worsening) is either during an infusion of study medication or within 72 hours of the end of the infusion. [Unit: N/A]
- The **rate of absence from work or study** will be based on the assumption of 200 working/study days per year, i.e. the rate is to be calculated as $R = (1/200) * (\text{Number of days absent from work or study}) / (\text{Patient years on octanorm treatment})$ [Unit: 1/years]

9. Study Subjects and Demographics

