All absences from work or study will be listed with duration and reason for absence. The individual absence rates per person-year will be calculated and summarized by descriptive statistics.

11. Safety and Tolerability Analyses

The safety analysis will comprise descriptive statistics, tabulations and listings of all TEAEs, safety laboratory results, viral markers, vital signs and physical examination findings.

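### The work/study absence rate is a unitless share of a 200-day year labelled 1/years, and it counts absences from any cause although the endpoint is limited to infections

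*SAP*

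**What the plan says.** Section 3.2.2 lists as a secondary efficacy endpoint "Days missed from work/study due to infections and their treatment".

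Section 8.3 gives the derivation of an absence variable R, which "will be based on the assumption of 200 working/study days per year, i.e. the rate is to be calculated as" a quotient multiplied by 1/200. The numerator of that quotient is "Number of days absent from work or study" and its denominator is "Patient years on octanorm treatment". The unit is stated as 1/years.

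Section 10 (Efficacy Analysis) describes the output in two sentences: "All absences from work or study will be listed with duration and reason for absence", followed by "The individual absence rates per person-year will be calculated and summarized by descriptive statistics".

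Section 8.3 assigns units to its other rates as well. The serious bacterial infection rate, a count over person-time, carries 1/years. The proportion of infusions with a temporally associated adverse event, a count over a count, carries no unit; that entry ends "within 72 hours of the end of the infusion. [Unit: N/A]".

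**The concern.** There are two separate faults in the same derived variable.

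- **Scale.** The constant 200 is introduced as a number of days per year. Dividing an annualised number of days by it gives a fraction of working or study time lost. That is a reasonable quantity to report, but it is not a rate per year. The unit in section 8.3 and the per-person-year wording in section 10 both invite the reader of the study report to take it as one.
- **Numerator.** The endpoint is confined to days lost through infection and its treatment. Neither the formula nor the section 10 text carries that restriction. Programmed as written, R is all-cause absence, and no planned summary matches the endpoint as defined. Days lost for unrelated reasons would count towards an efficacy measure of infection burden.

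**Working it through.** **Inputs**

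- Working or study year: 200 days per year (section 8.3).
- Numerator: days absent, with no restriction by cause (section 8.3).
- Denominator: patient-years on octanorm (section 8.3).
- Observation time for a completer: section 5.1 gives treatment "over a total period of approximately 32 weeks". Section 4.1 agrees: 32 weekly infusions place the last one 31 weeks after the first, and the final examination follows 1 week later, so 31 + 1 = 32 weeks.
- Days absent, and how many are due to infection: not given in the SAP. The values below are assumptions for illustration.

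The SAP states no numerical absence rate, so the stated figure to test is the unit.

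**Step 1: the unit of R**

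Unit of R = [1 / (days/year)] × [days] / [years] = [years] / [years], which is unitless.

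The stated unit, 1/years, is obtained only if 200 is treated as a bare number and days as unit-free counts.

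**Step 2: what R measures**

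T = 32 × 7 / 365.25 = 0.6133 years.

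Expected working or study days in T = 200 × 0.6133 = 122.7.

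A patient absent on every one of those days has R = 122.7 / (200 × 0.6133) = 1.0. R is therefore the share of expected working time lost, with 1.0 meaning all of it. In days per person-year the same patient has 122.7 / 0.6133 = 200.

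**Step 3: the two scales for an assumed 5 days absent**

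- Days per person-year: 5 / 0.6133 = 8.15.
- R as defined: 8.15 / 200 = 0.041, or 4.1% of a 200-day year.

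The two scales always differ by the factor 200.

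**Step 4: the effect of the unrestricted numerator**

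The total is kept at 5 days absent, and the number due to infection or its treatment is varied.

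| Infection-related days (assumed) | Endpoint, days per person-year | Endpoint as a share of a 200-day year | R as written |
|---|---|---|---|
| 1 | 1 / 0.6133 = 1.63 | 0.008 | 0.041 |
| 3 | 3 / 0.6133 = 4.89 | 0.024 | 0.041 |
| 5 | 5 / 0.6133 = 8.15 | 0.041 | 0.041 |

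The formula gives the same answer in all three rows. It matches the endpoint only when every absence is due to infection.

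**Step 5: whether the restriction is supplied elsewhere in the SAP**

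The diary items in section 4.1 include missed days in general, with no cause attached. Section 10 starts from all absences and lists a reason for each, which implies that reasons differ. It then calculates the rates with no filter on that reason. Nothing in the SAP narrows the numerator.

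**The case against.** On the unit, it can be said that this is notation. The formula is printed in full, and any two programmers would compute the same number. Section 8.3 treats infections as unit-free counts, and if days are treated likewise and 200 is a plain constant, 1/years follows. The infusion ratio without a unit has no time term, so it is an imperfect comparator. A value near 0.04 is also unlikely to be mistaken for days per year by an attentive reader. Some of this stands: the computed value is unambiguous, and the 200-day normalisation is legitimate. The bare-constant reading, however, conflicts with the SAP's own description of 200 as days per year. It also leaves a quantity that is neither days nor events per year.

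On the numerator, the formula could be read together with section 3.2.2, because section 8.3 introduces its variables as serving the primary and secondary target variables. Section 8.3 also allows further derivations to be described in the study report. With about 20 to 25 patients, infection-related days could be picked out of the listing. The last point stands and limits the harm. The other two do not change the rule as written: the derivation names days absent without qualification, and leaving the filter to the study report means it is not specified in advance.

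It is also fair to say that the SAP does not show how the reason for absence is coded. That bears on the cost of the repair, not on whether the mismatch exists.

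**Conclusion.** Both points hold. R is a unitless proportion of an assumed 200-day year, carrying a unit and a description that belong to a rate. Read as days per person-year, it is too small by a factor of 200. Its numerator is all-cause absence, so it does not measure the secondary endpoint in section 3.2.2, and no other planned summary does.

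The factor of 200 follows from the formula alone. The size of the numerator error depends on the share of absences unrelated to infection, which the SAP does not give; the 5 days and the split of 1, 3 or 5 are illustrative assumptions.

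The consequence is limited. This is one descriptive secondary endpoint, section 10 states that no confirmatory efficacy analysis will be done, and the absence listing would let infection-related days be recovered. It should be corrected before the analysis is programmed.

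**What to change.** 1. In section 8.3, restrict the numerator to days absent because of infection or its treatment, identified from the reason for absence that section 10 already lists. State the same restriction in the section 10 sentence on individual rates. All-cause absence can remain in the listing.
2. Choose one scale and use it in both sections. Either drop the factor 1/200 and report days per person-year, or keep it and describe R in sections 8.3 and 10 as the proportion of working or study time lost, with no unit.
3. State how absences with a missing reason are handled.

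The cost is a short edit to the formula or its label, plus a filter in the program. Each absence must be classified as infection-related or not before the analysis. No new data should be needed, provided the reason is recorded in a form that allows this classification. Section 10 implies that a reason is recorded, but the SAP does not show how it is coded.
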